4.7.1.2. Secondary target variables

- Number of treatments with Ranibizumab up to 6, 12, 18 and 24 months of treatment respectively
- Mean average change in BCVA at 6, 12, 18 and 24 months after initial treatment
- Macular thickness (as measured with OCT) at 6, 12, 18, and 24 months after initial treatment
- Time to reach target HbA1c
- Number of neovascular complications: need for panretinal laser photocoagulation (PRP)
- Rates of ocular and of systemic AEs (retinal detachment, Central retinal artery occlusion, endophthalmitis; and rates of stroke, myocardial infarction, severe hypoglycemia)

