6.1.3. Primary target variable

The primary endpoint will be the change of best corrected visual acuity in ETDRS Letters score at month 12 when compared with baseline. This endpoint will be analysed by analysis of covariance (ANCOVA) with the baseline value as covariate (type II SS will be used since no interaction terms are included in the model).

The null hypothesis is:

$$H_0: \mu_{iDC} = \mu_{rDC}$$

and the alternative hypothesis is:

$$H_1: \mu_{iDC} \neq \mu_{rDC}$$

where μ_{iDC} is the mean of the differences in ETDRS Letters score between month 12 and baseline for the investigational arm (intensified diabetic control) and μ_{rDC} is the mean of the differences in ETDRS Letters score between month 12 and baseline for the control arm (regular diabetic control).

ITT population is used for the primary efficacy analysis. If no ETDRS Letter score is available at month 12 the closest measurement (could be before or after 12 month) which was at least after 3 months will be used for the analysis.

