6.1.4. Secondary efficacy variables

Different statistical methods will be applied for analysis of secondary endpoints.

For the number of treatments at 6, 12, 18 and 24 months, an ANOVA without any covariates will be applied at each endpoint 6, 12, 18 and 24 months.

The data of change in BCVA and macular thickness at 6, 12, 18 and 24 months are analysed by repeated measures analysis of variance (assuming missing at random, MAR). The missing values for BCVA and macular thickness are imputed by the last observation carried forward (LOCF). The treatment by time interaction will be included in both statistical models but the baseline value will only be included in the change in BCVA analysis since the macular thickness will not be adjusted by the baseline value in this analysis.

The change in BCVA and macular thickness with respect to baseline values is calculated at 6, 12, 18 and 24 months. For each time point, the change values are described statistically by mean, standard deviation, and 95% confidence interval.

Time to reach target HbA1c is evaluated by log-rank test and hazard ratio in terms of a Cox proportional hazard model. The results are visualised by Kaplan-Meier curves. No covariates are included in the model.

The number of neovascular complications in two treatment arms is compared by frequencies and a chi-square test if applicable (the chi-squared test will not be used when the absolute frequency in any of the cells of the contingency table is below 5), otherwise the Fishers exact test will be performed.

ITT population is used for all secondary efficacy analyses.

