6.1.8. Handling of missing data

If not stated otherwise no imputations of missing values will be performed.

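### Month-12 BCVA change is both the primary endpoint and one time point of a secondary endpoint, but a missing month-12 score is filled by a different rule in each, so the two month-12 results will very likely not match

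*Combined protocol and SAP*

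**What the plan says.** Section 6.1.3 defines the primary endpoint: "The primary endpoint will be the change of best corrected visual acuity in ETDRS Letters score at month 12 when compared with baseline". The model is stated as follows: "This endpoint will be analysed by analysis of covariance (ANCOVA) with the baseline value as covariate". It is run in the ITT population. If there is no month-12 score, "the closest measurement (could be before or after 12 month) which was at least after 3 months will be used for the analysis".

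Section 4.7.1.2 lists as a secondary variable "Mean average change in BCVA at 6, 12, 18 and 24 months after initial treatment". Section 6.1.4 makes clear that this is the same kind of change: "The change in BCVA and macular thickness with respect to baseline values is calculated at 6, 12, 18 and 24 months". The analysis is a repeated-measures ANOVA with a treatment-by-time interaction and, for BCVA, the baseline value. It also uses the ITT population and is described as assuming missing at random (MAR). Its rule for gaps is: "The missing values for BCVA and macular thickness are imputed by the last observation carried forward (LOCF".

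Section 6.1.8 adds a default: "If not stated otherwise no imputations of missing values will be performed". Both rules above are stated, so the default overrides neither. Section 6.1.6 names two sensitivity analyses of the primary endpoint (per-protocol and log-transformed). LOCF at month 12 is not one of them.

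**The concern.** One quantity, in one population and with the same baseline adjustment, is built in two ways, and nothing in sections 6.1 to 6.1.8 links them. A reader of the report would find the month-12 point of the 6-to-24-month course differing from the primary result in value and in number of patients, with both labelled ITT and no explanation. Section 6.1.6 repeats both analyses within subgroups, where one patient's value weighs more.

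The second issue is LOCF itself. It fills every gap by assuming that the score stays where it last was, which leaves the stated MAR assumption with nothing to do. Where patients leave early and vision is still changing, it carries a month-1 or month-2 score to month 12. If the arms lose patients early at different rates, that biases the secondary comparison.

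**Working it through.** **1. The plan's own figure.** Section 6.2 gives δ = 2.0, σ = 3.5, two-sided α = 5% and power 85%. The normal approximation gives n per arm = 2 × (1.960 + 1.036)² × (3.5/2.0)² = 2 × 8.978 × 3.0625 = 54.99, so 55. The noncentral t gives 56 (power 0.850), which is the plan's 112 in total; 56 × 1.07 = 59.9, so 60 per arm. Neither missing-value rule enters this calculation. For scale, the standard error of the arm difference at 60 per arm is 3.5 × √(2/60) = 0.64 letters.

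**2. The two rules side by side**, reading LOCF as running over the monthly visits:

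| Month-12 score missing because the patient | Section 6.1.3 uses | Section 6.1.4 uses |
|---|---|---|
| left for good after month 3 | last score | last score (same) |
| missed month 12, attended 11 and 13 | month 11 or 13 (no tie rule; actual dates may decide) | month 11 |
| missed 11 and 12, attended 13 | month 13 | month 10 |
| left before month 3 | no value | month-1 or month-2 score |

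The last three rows can occur. BCVA is measured monthly to month 24 (Tables 2 and 3). Visits after month 12 have a ±4-week window, so visit 13 can fall nearer month 12 than visit 11. The ITT set needs only one injection (section 6.1.1).

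**3. Size by hand.** Assumptions not in the documents: half of the 7% drop-outs leave before month 3; 5% of the remaining patients miss only visit 12; ties go to month 13; within-patient correlation of the changes is 0.7; the mean course is flat.

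- Early leavers: 60 × 0.035 = 2.1 per arm. Missed visits: 60 × 0.93 × 0.05 = 2.8 per arm. Together 2 × 4.9 = 9.8, about 10 of 120 patients.
- Month 13 in place of month 11: SD per patient 3.5 × √(2 × 0.3) = 2.71. Per arm 2.71 × √2.8 / 57.9 = 0.078. For the arm difference × √2 = 0.11.
- Early leavers in one analysis only: per arm (2.1/60) × 3.5 × √(1/2.1 + 1/57.9) = 0.086. For the arm difference × √2 = 0.12.
- Combined SD of the gap: √(0.11² + 0.12²) = 0.16 letters, a quarter of the standard error (0.16/0.64).

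**4. Size by simulation** (60 per arm, difference 2.0, SD 3.5; all else assumed). Discordance means that one rule gives p < 0.05 and the other does not, if a month-12 contrast is tested under both.

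- Inputs of step 3, flat course: SD 0.17 letters, discordance 4.6%.
- Same inputs with a rising mean course: SD about 0.25, discordance about 9%.
- AR(1) correlation 0.9, ties at random, 20% of drop-outs early: SD 0.10, discordance 2.7%.
- A separate run with 7% missing month 12, AR(1) 0.9 and random ties. The 95th percentile of the absolute gap is 0 if all leave after month 3, 0.14 if all miss only visit 12, 0.53 if all leave before month 3, and 0.27 for a 25% early leavers / 50% late leavers / 25% missed-visit mix (discordance about 3%).

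**5. Unequal early drop-out.** Assume that all drop-out occurs before month 3 and is unrelated to outcome, that the control mean follows 6 × (1 − e^(−t/3)), and that the treatment effect grows linearly to 2.0 at month 12.

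- Control: months 1 and 2 average (1.70 + 2.92)/2 = 2.31; month 12 is 5.89; shortfall 3.58.
- Intensified arm: extra shortfall 2.0 − (0.17 + 0.33)/2 = 1.75; total 5.33.
- 15% lost in the intensified arm, 5% in control: LOCF expectation 2.0 − 0.15 × 5.33 + 0.05 × 3.58 = 1.4.
- The reverse: 2.0 + 0.15 × 3.58 − 0.05 × 5.33 = 2.3.

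The 6.1.3 rule drops these patients and stays at 2.0 under the same assumptions.

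**6. What remains under one common rule.** ANCOVA and a repeated-measures model with one baseline slope still differ slightly on complete data: 95th percentile about 0.07 letters. Rule-driven differences vanish.

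**The case against.** The strongest reply is that nothing confirmatory is at risk. Section 6.1.3 fixes the endpoint, model, population and fallback rule; section 6.1 attaches the 5% level to the primary analysis; section 6.1.4 concerns secondary variables and says that methods will differ. This stands. A reader might infer that the primary result is ambiguous, but the documents do not support that.

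Nor does 6.1.4 state a month-12 test. It specifies one model over four time points and, per time point, only a mean, SD and confidence interval. A reader might infer two competing month-12 p-values; the text does not promise them. The discordance figures are therefore conditional on such a contrast being tested.

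A mismatch is also not certain. Patients who leave for good after month 3 get the same value under both rules. Section 4.4 asks for follow-up after treatment is discontinued, which argues against a large share of early losses. That share drives the size of the gap and has no source in the documents.

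Finally, 6.1.4 does not say whether LOCF runs over monthly visits or only over months 6, 12, 18 and 24. The table above is one reading. The other could widen the gap: a patient last seen at month 10 would contribute month 10 to 6.1.3 and month 6 to 6.1.4.

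These points limit the consequence. They do not reconcile the two rules.

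**Conclusion.** The inconsistency is real and rests on the text alone. With 120 patients and monthly visits, at least one missed month-12 visit followed by a return, or one departure before month 3, is very likely, so the two month-12 results will very likely differ in value or patient number. It is wrong to say that they must.

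At about the planned 7% drop-out the effect is small: SD of the gap about 0.1 to 0.25 letters, and significance differing in roughly 3 to 9% of simulated trials if a month-12 contrast is tested. The range reflects assumed missingness, correlation, tie-breaking and mean course. With assumed early drop-out of 15% v 5%, LOCF biases the secondary month-12 difference by about 0.3 to 0.6 letters, in a direction set by which arm loses more patients.

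The primary analysis and the sample size are unaffected. This is a fault of consistent reporting and of the secondary analysis.

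**What to change.** In section 6.1.4, or in the separate analysis plan to which section 6.1 defers detail:

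- Delete LOCF for BCVA and fit the repeated-measures model to the observed scores, under the MAR assumption already stated there.
- State that the 6.1.3 ANCOVA is the only month-12 BCVA comparison between arms, and that the repeated-measures model supplies months 6, 18 and 24. Observed month-12 scores can stay in the model as data.
- If LOCF at month 12 is kept, name it as a sensitivity analysis and say which visits it carries from.
- In 6.1.3, say how a tie between months 11 and 13 is broken and what happens to an ITT patient with no score from month 3 on.

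The primary ANCOVA need not be replaced. Making a repeated-measures contrast the primary result would be a larger, debatable change that this problem does not require. The cost is minor rewording, with no new data and no change in sample size.

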4.7.3. Optical Coherence Tomography (OCT)

A Spectral Domain OCT of Heidelberg Engineering (Spectralis, Heidelberg Engineering, Heidelberg, Germany) should be used to perform the measurements at every time point indicated in the visit schedule. OCT macular volume scans of both eyes should be performed.

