6.1.6. Sensitivity and Subgroup analyses

A sensitivity analysis for the primary endpoint based on the PP population will be performed.

Another sensitivity analysis will assess the influence of the assumption of normality for the primary analysis by transforming the data with the natural logarithm. The ANCOVA described in section 6.1.3 will be applied in the same way on the transformed data.

The primary and secondary endpoint except number of neovascular complications and rates of ocular and of systemic AEs will be analysed by descriptive statistics and statistical methods mentioned above within the following subgroups defined by the following potentially prognostic baseline variables:

- HbA1c: $\geq 9\%$
- HbA1c: $\geq 7,5\%$, $< 9\%$

- HbA1c: $\geq 6,5\%$, $< 7,5\%$
- Intravitreal treatment with ranibizumab before trial entry (yes vs no)
- Size of macula edema $>400\mu\text{m}$
- BCVA (>65 vs ≤ 65)

For the sake of subgroup analysis, the ITT population will be used.

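### The macular thickness model leaves out baseline thickness, although it is already measured; this does not in itself bias the comparison, but it costs precision

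*Combined protocol and SAP*

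**What the plan says.** Section 6.1.4 plans a repeated-measures analysis of variance with a treatment-by-time term for BCVA and for macular thickness. The baseline value enters the BCVA model only; for the other, "the macular thickness will not be adjusted by the baseline value in this analysis". That clause is offered as the reason for the difference, but it only restates the decision.

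The primary endpoint is handled the other way. Section 6.1.3 specifies "analysis of covariance (ANCOVA) with the baseline value as covariate".

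Baseline thickness is available. Table 2 (Section 4.7.4.1) marks OCT at screening and again at visit 1, and a minimum central retinal thickness is an inclusion criterion (Section 4.3.1). Section 6.1.6 lists oedema size above 400 µm among subgroups "defined by the following potentially prognostic baseline variables".

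The outcome being modelled is not settled either. Section 4.7.1.2 defines the endpoint as a level: "Macular thickness (as measured with OCT) at 6, 12, 18, and 24 months after initial treatment". Section 6.1.4 opens with "The data of change in BCVA and macular thickness at 6, 12, 18 and 24 months", which can be read as change in both measures.

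**The concern.** In a randomised trial, adjusting a continuous outcome for its own baseline is a standard way to gain precision. The plan does so in both BCVA analyses and declines to do so for thickness without an argument.

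Two things are at stake. First, the interval for the thickness difference will be wider than the collected data allow. Second, any chance baseline difference in the one sample obtained carries into the estimate: uncorrected if levels are modelled, over-corrected if changes are modelled. Allocation is unstratified (Section 4.2), so the design does not balance thickness.

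Nothing else in the plan fills the gap. The baseline summaries by arm (6.1.2), the descriptive changes (6.1.4) and the subgroup above 400 µm (6.1.6) all show baseline information, but none yields a baseline-adjusted difference between arms. Section 6.1.6 also reuses the same methods within subgroups, where chance imbalance is larger.

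**Working it through.** **The plan's own figure.** There is none for thickness. The only sample size is for BCVA (Section 6.2: difference 2.0, SD 3.5, two-sided 5%, power 85%). It reproduces: 56 per arm gives 85.0% power by the t-test, and 56 × 1.07 = 59.9, hence 60 per arm. It does not bear on the thickness model.

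**Inputs.** 60 per arm, 1:1 (Sections 4.2 and 6.2). The correlation r between baseline and follow-up thickness is not in the documents; 0.2 to 0.7 is assumed. The ratio k of follow-up SD to baseline SD is also assumed, first as 1.

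**Variance of the unadjusted difference divided by that of the adjusted one, at a single visit.**
- Levels: 1/(1 − r²), whatever k is.
- Changes: (1 + k² − 2rk)/(k²(1 − r²)), which is 2/(1 + r) when k = 1.
- The ratio of interval widths is the square root.

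| r | Levels: variance ratio | Interval wider by | Changes, k = 1: variance ratio | Interval wider by |
|---|---|---|---|---|
| 0.2 | 1.04 | 2% | 1.67 | 29% |
| 0.3 | 1.10 | 5% | 1.54 | 24% |
| 0.5 | 1.33 | 15% | 1.33 | 15% |
| 0.7 | 1.96 | 40% | 1.18 | 8% |

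For r = 0.3, 0.5, 0.7 the change ratios become 2.40, 2.15, 2.04 if k = 0.7, and 1.24, 1.10, 1.01 if k = 1.3.

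The level ratio rises with r and, at k = 1, the change ratio falls; they meet at r = 0.5. With equal SDs, therefore, no r makes both readings harmless: the larger ratio is never below 1.33.

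**The level loss in patients.** Matching 112 patients analysed with adjustment would take 112/(1 − r²) without it: 112/0.91 ≈ 124, 112/0.75 ≈ 150, 112/0.51 ≈ 220. For an illustrative true difference of 0.4 SD at 56 per arm, power is 55.5% unadjusted, against 59.5%, 67.8% or 83.6% adjusted.

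**The same loss, given the imbalance that occurs.** A baseline difference of d SD shifts the expected estimate by r × d (levels) or −(1 − r) × d (changes, k = 1), and by about 0 after adjustment. One standard error of the baseline difference is √(2/60) = 0.183 SD. For r from 0.3 to 0.7 the shift is 0.055 to 0.128 SD (levels) or −0.128 to −0.055 SD (changes). In a subgroup with an assumed 20 per arm, the standard error would be √(2/20) = 0.32 SD.

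**Check on bias and type I error.** In 5,000 simulated complete-data trials per setting at 56 per arm, the unadjusted level comparison rejected a true null in 4.6%, 5.0% and 5.5% of trials at r = 0.3, 0.5, 0.7 (adjusted: 4.3%, 5.2%, 4.8%). With a true difference of 0.4 SD, both estimates averaged 0.40. The standard deviations of the estimates, unadjusted against adjusted, were 0.187 against 0.180, 0.192 against 0.167, and 0.188 against 0.135.

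**The case against.** The strongest reply is that this is a pre-specified choice on one secondary endpoint of an exploratory trial, with a cost of unknown size. The documents give no r. The entry floor on thickness, and the treatment of every patient for the oedema, could make r low by months 6 to 24; at r = 0.2 the level interval is only about 2% wider. Level is also the better-supported reading: the endpoint definition says so, and Section 6.1.4 deals with change in thickness in a separate descriptive paragraph. The larger change ratios should therefore not drive the judgement. Oedema size appears as a subgroup variable across several endpoints, which is only indirect evidence that it predicts later thickness.

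Much of this stands. The direction of the effect is certain; its size is not. The absence of bias also concerns the omission of baseline only. Last-observation imputation under a stated missing-at-random assumption (6.1.4), and discontinuation for lack of thickness reduction (4.4), are separate matters that the calculation does not cover.

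It does not rescue the exclusion. A low r helps only if levels are modelled, and the wording leaves that open. Section 6.1 defers further details to a statistical analysis plan, but the exclusion is an explicit instruction, not a detail left open.

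**Conclusion.** The concern holds. The plan discards a baseline value available for every eligible patient, without a reason and against its own practice for BCVA. Leaving it out does not itself bias the randomised comparison. The price is precision: for levels, an interval about 5% to 40% wider for assumed r of 0.3 to 0.7, and about 2% at r = 0.2; for changes with equal SDs, about 24% down to 8% over the same 0.3 to 0.7. These are per-visit figures that rest on assumed r and, for changes, on the assumed SD ratio. The primary analysis and the sample size are unaffected. The change should be made because it uses data already collected and helps under either reading of the outcome.

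**What to change.** In Section 6.1.4, replace the exclusion with a statement that continuous baseline central retinal thickness is a covariate in the repeated-measures model for macular thickness. In the same place:

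- State whether level or change is the outcome. Once baseline is in the model, the between-arm differences are the same either way.
- Name the OCT that serves as baseline, screening or a pre-injection scan at visit 1.
- Report adjusted between-arm differences with 95% confidence intervals at 6, 12, 18 and 24 months.

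A baseline-by-visit term is preferable, since r may fall from month 6 to month 24, but it goes beyond the stated BCVA model and is optional.

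The cost is one or two sentences and no new data: one degree of freedom for baseline alone, or about four with baseline-by-visit over four visits. If the sponsor prefers to keep the exclusion, the plan should give a reason for it.

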4.4. Withdrawal of trial subjects after trial start

Study subjects will be early discontinued from participation in the study if

- they withdraw consent from participating in the study
- no response to the ranibizumab treatment is observed, defined as persisting macular edema without any reduction of central retinal thickness after 3 consecutive monthly injections
- they present visual loss defined as ≥ 30 ETDRS Letters when compared with the baseline
- they develop vitreous bleeding due to active neovascularisation of the retina or optic disc confirmed by fluorescein angiography with need of surgical treatment (vitrectomy)
- any other clinical adverse event (AE), laboratory abnormality, illness or other medical condition or situation occurs that would not go along with the best interest of the patient in case of continuing the participation.

Note: Each patient should be followed-up even if the study treatment is discontinued.

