6.1.1. Trial populations

The first dataset for analysis is derived from the intention-to-treat (ITT) population. This dataset includes all trial subjects enrolled into the trial, randomised to treatment groups and received at least one injection of ranibizumab- no exclusions.

The second dataset for analysis is derived from the per-protocol (PP) population. This dataset includes all trial subjects who were treated according to protocol (i.e. they received at least 3 injections of ranibizumab and do not meet any exclusion criteria) and reached/provided at least one endpoint of main interest (i.e. after 6 months of follow-up).

The third dataset for analysis is the safety population. This population includes all trial subjects who received any ranibizumab treatment.

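### Need for PRP is compared as raw frequencies, with no period and no time at risk, so unequal early exit between arms would bias the comparison in either direction

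*Combined protocol and SAP*

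**What the plan says.** Section 4.7.1.2 defines the endpoint through the need for laser ("Number of neovascular complications: need for panretinal laser photocoagulation (PRP"), with no month attached. The neighbouring endpoints do carry time points, for example "Number of treatments with Ranibizumab up to 6, 12, 18 and 24 months of treatment respectively". BCVA change and macular thickness have the same four.

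Section 6.1.4 gives the method: "The number of neovascular complications in two treatment arms is compared by frequencies and a chi-square test if applicable", otherwise Fisher's exact test, which applies when a cell of the table is below 5. It adds that "ITT population is used for all secondary efficacy analyses". Section 6.1.1 defines that set as patients "randomised to treatment groups and received at least one injection of ranibizumab- no exclusions". On missing data, section 6.1.8 says: "If not stated otherwise no imputations of missing values will be performed". LOCF is stated only for BCVA and macular thickness.

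Survival methods appear in the same section for another endpoint: "Time to reach target HbA1c is evaluated by log-rank test and hazard ratio in terms of a Cox proportional hazard model".

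On leaving the trial, section 4.4 opens its list with "Study subjects will be early discontinued from participation in the study if". The list includes lack of response after three injections, a loss of at least 30 letters, and neovascular vitreous bleeding that needs vitrectomy. A note at the end of 4.4 asks for follow-up of every patient even when study treatment stops. Section 4.2 plans active follow-up by a study nurse or physician. Section 4.6.8.1 allows a patient to be withdrawn from the study if patient or physician finds the effect insufficient.

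**The concern.** Need for PRP accumulates over 24 months, so the chance of recording it depends on how long a patient is watched. A plain two-by-two table ignores this. No rule says how a patient who leaves without PRP is classified. With every ITT patient in the denominator and nothing imputed, such a patient falls into the no-event cell beside patients observed for the full two years. With no period stated, a 12-month and a 24-month comparison would both comply with the plan.

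Unequal exit is plausible. Treatment is open (section 4.6.7), and several exit routes depend on poor response or on judgement. Less frequent ocular complications are part of the trial's stated aim (section 1), so the estimate for this endpoint will be read. What is at stake is its size and, with a large imbalance, its test.

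**Working it through.** **1. The plan's own figures.** Section 6.2 gives a difference of 2.0, SD 3.5, two-sided alpha 5% and power 85%. The two-sample t-test gives 55.97, so 56 per arm and 112 in total, as stated. The drop-out allowance is 56 × 1.07 = 59.92, so 60 per arm. These figures are not in dispute. They supply n = 60 per arm and an anticipated drop-out of about 7%, not split by arm. The documents give no PRP rate and no exit rate by arm, so those below are assumptions.

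**2. Crude proportion when leavers count as event-free.** Let p be the true 24-month risk (constant hazard) and d the proportion leaving at month 3, unrelated to risk. Then

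crude = p(1 − d) + d[1 − (1 − p)^(3/24)].

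The three-month risks are 1 − 0.70^0.125 = 0.0436 and 1 − 0.88^0.125 = 0.0159.

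- Exits 20% control, 5% intensified: 0.30 × 0.80 + 0.20 × 0.0436 = 0.2487, and 0.12 × 0.95 + 0.05 × 0.0159 = 0.1148. Difference 13.4 points.
- Exits 5% control, 20% intensified: 0.30 × 0.95 + 0.05 × 0.0436 = 0.2872, and 0.12 × 0.80 + 0.20 × 0.0159 = 0.0992. Difference 18.8 points.

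For the planned test, power is computed exactly: rejection (uncorrected chi-square, Fisher if any cell is below 5) is summed over all pairs of binomial counts with 60 per arm. For log-rank it comes from 20,000 simulated trials, with event times rounded up to the month.

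| True risks (control/intensified) | Exits (control/intensified) | Crude difference, points | Planned test rejects | Log-rank rejects |
|---|---|---|---|---|
| 30% / 12% | none | 18.0 | 69% | 69% |
| 30% / 12% | 20% / 5% | 13.4 | 47% | 65% |
| 30% / 12% | 5% / 20% | 18.8 | 75% | 63% |
| 30% / 12% | 7% / 7% | 16.9 | 65% | 67% |
| 30% / 12% | 10% / 4% | 15.9 | 60% | 67% |
| 30% / 12% | 4% / 10% | 18.0 | 71% | 66% |
| 30% / 30% | 5% / 20% | 3.8 | 7.9% | 4.6% |

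Simulations of 1,500 to 3,000 trials agree within sampling error: 13.5 to 13.6 points and 47% against 65–67% in the second row, 18.5 to 18.9 points and 74–75% against 62–63% in the third, and 61% against 68% for exits of 10% vs 4%.

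With no exits the two tests have the same power, so the gap comes from exit, not from log-rank being the stronger test. The 75% in the third row is no merit: the same mechanism produces the false difference in the last row.

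**3. Exits spread over the 24 months.** With λ = −ln(1 − p)/24 and μ = −ln(1 − d)/24,

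crude = λ/(λ + μ) × [1 − exp(−24(λ + μ))].

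Take risks of 20% vs 10%, a true difference of 10.0 points. For the control arm with 30% exits: 0.2231/0.5798 × (1 − exp(−0.5798)) = 0.1693. The results are:

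- exits 30%/10%: 16.93 − 9.50 = 7.4 points
- exits 10%/30%: 19.02 − 8.44 = 10.6 points
- exits 7%/7%: 19.32 − 9.65 = 9.7 points, ratio 0.50

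The pattern is the same: the sign of the bias follows the imbalance, and equal exit near 7% costs little.

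**The case against.** The best defence is that the plan foresees little loss of observation. The note in section 4.4 and the active follow-up in section 4.2 mean that a patient who stops ranibizumab but stays under observation loses no time at risk. Section 6.2 expects about 7% drop-out. With a fixed 24-month schedule, a cumulative proportion with a chi-square or Fisher test is a conventional choice. Section 6.1 also leaves further details to a statistical analysis plan.

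Much of this stands. It limits the problem to patients truly lost, those who withdraw consent, and those withdrawn from the study as 4.6.8.1 allows. It is not complete protection, because the list in 4.4 speaks of participation in the study while its note speaks of study treatment. The 20% vs 5% exits, all at month 3, lie well above the planned rate and are unfavourable by construction.

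A reader might also infer three stronger things that the documents do not support:

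- **That unequal exit always dilutes a real benefit.** It does so only if the higher-risk arm loses more patients; the reverse imbalance overstates the benefit.
- **That the plan declares leavers complication-free.** This is an inference from an ITT set without exclusions and a frequency table. The alternative, leaving them out as missing, fits poorly with a set that allows no exclusions. The plan does not settle it.
- **That log-rank cures the problem.** The gains above assume exits unrelated to risk. Exit for neovascular bleeding that needs vitrectomy is tied to the disease behind the endpoint, and censoring it as uninformative would be wrong.

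**Conclusion.** The point holds in limited form. The PRP comparison has no stated period and ignores time at risk, and unequal loss between arms would bias it either way. A 15-point imbalance in early exit moves an assumed 18-point difference to about 13.5 or about 18.8 points. With no true difference it creates a false one of about 3.8 points, and the rejection rate rises to about 8%. Near 7% drop-out the effect is small: power of 65% against 67% with equal exits, and 60–61% against 67–68% with 10% vs 4%. These sizes rest on assumed event rates, exit rates and exit times, a constant hazard, and leavers being counted as event-free. The endpoint is secondary, the trial is exploratory, and the primary analysis is untouched, so severity is minor.

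**What to change.** In section 6.1.4, analyse time from randomisation to the first need for PRP, one event per patient, up to month 24, censored at the last funduscopy. Use the log-rank test, and report Kaplan-Meier 24-month risks by arm with their difference and 95% CI. Keep the frequency table as description.

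Add a sensitivity analysis that counts exit for neovascular vitreous bleeding needing vitrectomy as an event. This is an analysis rule only and changes nothing in patient management.

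The cost is wording. Laser treatment is already recorded in the database/CRF (section 4.6.8.1), and the section already uses these methods for HbA1c. There are two downsides: event dates may be known only to the nearest visit, and the log-rank analysis assumes that the remaining exits are unrelated to risk. Continued follow-up of patients who stop treatment is therefore still needed.
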